9.1 Efficacy Parameters/ Assessments

9.1.1 Polysomnography (PSG)

PSG is the gold standard for the objective assessment of sleep parameters. The Interdisciplinary Center for Sleep and Ventilatory Medicine at the Jena University Hospital is certified by the German Sleep Medicine Society (DGSM) and follows the recommended diagnostic and therapeutic standards.

During PSG brain activity (electroencephalogram, EEG), eye movement (electro-oculogram), muscle activity (electromyogram) and cardiac activity (electrocardiogram) as well as respiratory parameters (airflow, respiratory effort, and oximetry) will be recorded.

Sleep efficiency (SE) is calculated as the ratio of total sleep time (TST) to time in bed (TIB) (i.e., both sleeping and attempting to fall asleep or fall back asleep). Sleep onset latency (SOL) is the time in minutes from 'lights out' to the first sequence scored as sleep. The sleep time in minutes on each sleep phase S1, S2, S3 and rapid eye movement (REM) are recorded. Total sleep time (TST) is the total amount of sleep time summarized of different sleep stages during the total recording time (time in bed, TIB). Periods of wakefulness occurring after the onset of sleep are defined as wake after sleep onset (WASO). The number of awakenings (NWAK) are counted.

Patients will spend 2 nights each onsite in the sleep laboratory for PSG adaptation (Baseline 1 and Visit 1) and for PSG (Baseline 2 and Visit 2). PSG measurements recorded during adaptation nights will not be used for primary and secondary endpoints but analyzed on exploratory basis only.

Daytime napping is not allowed before and after PSG nights. With urine and breath alcohol tests, patients will be screened for drug abuse and alcohol at Screening Visit and prior to PSG nights at Baseline 1, Baseline 2, Visit 1 and Visit 2.

9.1.2 Resting State Stress Response

Resting state stress response will be assessed based on the stress biomarkers cortisol, alpha-amylase and dehydroepiandrosterone sulfate (DHEA-S) in saliva samples.

Around 0.5 to 1 ml of saliva are to be collected at each of 5 time points starting immediately after awakening from PSG adaptation nights (Baseline 1/ Day -1 and Visit 1/ Day 13) and PSG nights (Baseline 2/ Day 0 and Visit 2/ Day 14) followed by sampling at 15 minutes, 30 minutes, 45 minutes and 60 minutes after awakening for the assessment of Cortisol Awakening Response (CAR).

To assess a diurnal profile of stress markers 4 additional saliva samples (around 0.5 to 1 ml/ sample) are to be collected at 4 time points at 3-hourly intervals over 12 hours at Baseline 1/ Day -1 and Visit 1/ Day 13 (Table 4).

Table 4: Resting state saliva sampling

Cortisol Awakening Response					Diurnal Profile*			
After awakening	+15 min	+30 min	+45 min	+60 min	+3 h	+6 h	+9 h	+12 h
X	X	X	X	X	X	X	X	X

*Only at Baseline 1 and Visit 1.

Saliva samples are collected in 2 ml SaliCap sampling tubes (TECAN/ IBL International, Hamburg, Germany, ref. no. RE69985) using short drinking straws. One sample of 0.5 to 1 ml saliva is sufficient to analyze cortisol, alpha-amylase and DHEA-S.

After instruction by the site personnel, samples are collected independently by each trial participant. Salivary samples are stored frozen at -80°C (+/- 10°C fluctuation) for interim storage (approximately 3 months) at the biobank of the local laboratory of the investigational site (Institut für Klinische Chemie und Laboratoriumsdiagnostik, IKCL, Jena University Hospital) before shipping to the saliva biomarker laboratory.

Stress parameter levels in saliva will be analyzed at Dresden LabService GmbH, Dresden, Germany, using commercial immunoassays from IBL International, Hamburg, Germany (i.e., Cortisol Saliva Luminescence ImmunoAssay (CLIA); and DHEA-S Saliva Enzyme-Linked Immunosorbent Assay (ELISA) following manufacturer's instructions. Saliva alpha-amylase will be analyzed following the method of Rohleider and colleagues (Rohleider, Nater et al. 2004).

9.1.3 Electroencephalography (EEG)

Electroencephalography (EEG) is a widely used technique to investigate human brain functioning.

In addition to EEG recordings during PSG nights, patients will undergo continuous EEG measurements at Baseline 1 (Day -1) and Visit 1 (Day 13). These include a resting-state EEG before the CPT, an EEG recording during the CPT, and a resting-state EEG after the CPT.

Changes in time course of EEG vigilance fluctuations during wakefulness will be assessed by VIGALL version 2.1 (validated with the Multiple Sleep Latency Test (MSLT) by Olbrich et al. 2015) at Visit 1 compared to Baseline 1. EEG asymmetry index results from the subtraction of the alpha's power natural logarithm of the right hemisphere from that of the left hemisphere and represents a robust stress feature (Giannakakis, Grigoriadis et al. 2015). Changes in the EEG asymmetry index at Visit 1 will be compared to Baseline 1.

Regional changes in spectral characteristics of EEG using relative power indices in delta-theta-alpha-beta frequency ranges are assessed.

9.1.4 Heart Rate (HR), Heart Rate Variability (HRV) and Electrodermal Activity (EDA)

The two peripheral branches of the autonomic nervous system (ANS), the parasympathetic and the sympathetic system, modulate the intrinsic activity of the cardiac pacemaker cells in the sinoatrial node. While the parasympathetic or vagal activity reducing energy expenditure is anabolic and health promoting, the sympathetic branch is needed for an adequate stress response. Thus, the heart rate and its variability mirror the resulting homeostasis of an organism influenced by physical as well as by psychological variables, such as stress in a certain environment.

The control of cardiovascular function is critical to adaptive behavior and can be measured by heart rate variability (HRV) reflecting dynamic interactions between excitatory and inhibitory autonomic control mechanism. The following HRV parameters will be selected:

- RMSSD (Root Mean Square of Successive Differences) as an index of parasympathetic activity in the time domain
- Baevsky's stress index (SI) as an index of sympathetic activity

- LF/HF (low frequency/ high frequency power) ratio as a frequency-based feature for sympathovagal balance.

Electrodermal activity (EDA) is a measure of changes in conductance at the skin surface due to sweat production, which is sympathetically controlled. It is therefore considered a sensitive measure of stress by reflecting activity within the sympathetic branch of the ANS.

HR, HRV and EDA will be assessed in resting state during rsEEG and under stress response during CPT as well as during sleep in the PSG (only HR and HRV indices).

9.1.5 Actigraphy

After patients have given their informed consent, they will receive and wear continuously (day and night except during PSG) an actigraphy watch (Actiwatch Spectrum Plus, Philips GmbH), which will continuously monitor movement information over the whole trial duration (Screening Visit/ Day -28 to -8 until Follow-up Visit/ Day 28) to assess SE, SOL, WASO, TST and NWAK as well as to track daily activity to investigate habitual sleep–wake patterns. At Screening Visit patients will be asked whether they will accept to continuously (day and night) wear the actigraphy watch around their wrist. Actiwatch is a water-resistant medical device that continuously records motion and light.

9.1.6 ePRO Designed Stress Questionnaires (EMAs)

Patients perceived stress levels (using Ecological Momentary Assessments, EMAs) will be reported by the patients inside the **AMS-ePRO®** which can be accessed via the patients' own smartphone, tablet or laptop (Bring Your Own Device = BYOD). Patients will report their stress levels daily over the whole clinical trial duration (Screening Visit until Follow-up Visit/ Day 28).

The site staff will assist patients with the installation of the app and give instructions for use.

9.1.7 Cold Pressor Test (CPT)

The CPT is used to induce a stressor and to assess the patients' stress response. CPT involves placing a hand or forearm in cold water (~0°C), a stimulus that induces stress response as pain is slowly increasing from mild to moderate intensity and is terminated by the patient by voluntary withdrawal of the limb.

CPT will be performed twice with each patient during this trial, following PSG adaptation nights at Baseline 1 (Day -1) and at Visit 1 (Day 13).

During CPT an EEG is performed to assess changes in EEG vigilance fluctuations, in the EEG asymmetry index and spectral characteristics of EEG due to stress induction. The patients' heart rate, HRV and EDA are measured during CPT to assess changes in the autonomic stress response.

Before conduction of the CPT (baseline), 20 minutes and 50 minutes after CPT blood (12.5 ml/ blood sample) will be taken to assess cortisol and DHEA-S, adrenalin and noradrenalin and inflammatory response (IL-6 and TNF- α).

Patients will complete a subjective pain rating questionnaire to measure the individual pain level during CPT on a numeric rating scale (0 to 10). Pain tolerance will be measured by the amount of time the patient spent with the hand or forearm in ice water.

9.1.8 Blood Samples for Stress Response

At Baseline 1 (Day -1) and Visit 1 (Day 13) patients will have repeated blood sampling.

Blood samples will be collected totally 6 times (3 times at each CPT) to assess stress response based on the assessment of biomarkers cortisol, DHEA-S, adrenaline and noradrenaline levels as well as to assess the inflammatory response based on IL-6 and TNF- α .

Each blood sample consists of 12.5 ml blood that will be split up in 3 monovettes (all from Sarstedt, Nümbrecht, Germany) as following:

- 4.9 ml blood will be collected in an S-Monovette® Serum Gel (ref no 04.1935.001) for the analysis of cortisol, DHEA-S and TNF- α ,
- 4.9 ml blood will be collected in an S-Monovette® K3 EDTA (ref no 04.1931.001) for the analysis of adrenalin and noradrenalin, and
- 2.7 ml blood will be collected in an S-Monovette® Lithium-heparin gel (ref no. 04.1928.001) for the analysis of IL-6.

Blood biomarker samples will be analyzed at the local laboratory of the investigational site (Institut für Klinische Chemie und Laboratoriumsdiagnostik IKCL, University Hospital Jena).

9.1.9 Sleep Diary

After patients have given their informed consent, they will receive access to an electronic sleep diary (adapted from DGSM - Deutsche Gesellschaft für Schlafforschung und Schlafmedizin, on **AMS-ePRO®**), which they are asked to complete every day starting at Screening Visit (Day -28 to -8) in the evening until End of Trial (Follow-up Visit/ Day 28). Beside subjective sleep parameters patients will also report their daily intake of IMP, adverse events and concomitant medication, if any.

9.1.10 Neuropsychological Tests (TAP)

With neuropsychological tests the Investigator assesses the patients' alertness, vigilance and sustained attention. These tests will be performed at Baseline 1 and at Visit 1 and last approximately 60 minutes. The electronic Tests of Attentional Performance® (TAP; Zimmermann and Fimm 2002) version 2.3.1 will be used to investigate changes in the alertness, vigilance and sustained attention (three subtests of the TAP).

9.1.11 Urine Test and Alcohol Breath Test

Urine drug screening test and an alcohol breath test will be performed at Screening Visit (Day -28 to -8) and prior to the PSG nights (Baseline 1, Baseline 2, Visit 1 and Visit 2).

9.1.12 Pregnancy Test

Urine pregnancy test will be performed at Screening Visit/ Day -28 to -8 in women with childbearing potential.

9.1.13 Blood Pressure

Blood pressure will be measured at Screening Visit to assess the patients' eligibility. The blood pressure will be measured at rest (patient should be at rest for at least 20 minutes). Measurement will be repeated 3 times with a break of 1 minute in between each measurement. The last measured systolic value will be taken to assess eligibility (see exclusion criterion no. 18).

Blood pressure measurements for the assessment of vital signs will be performed correspondingly.

9.1.14 Patient Questionnaires

Patient-Reported Outcomes (PROs) will be used in this trial to assess insomnia, the patients' perceived stress level and the patients' quality of life. Patients will complete the following questionnaires twice, at Baseline 1 (either in the evening prior to Baseline 1 PSG night or next morning following Baseline 1 PSG night) and either at Visit 1 (either in the evening prior to Visit 1 PSG night or next morning following Visit 1 PSG night), or at Follow-up Visit.

9.1.14.1 Pittsburgh Sleep Quality Index (PSQI)

The Pittsburgh Sleep Quality Index (PSQI) is a self-rated questionnaire which assesses sleep quality and disturbances. Nineteen individual items generate 7 component scores: subjective sleep quality, sleep latency, sleep duration, habitual sleep efficiency, sleep disturbances, use of sleeping medication, and daytime dysfunction. The PSQI is well suited for measuring change in insomnia and will be completed on paper at Baseline 1 and at Follow-up Visit.

9.1.14.2 Insomnia Severity Index (ISI)

The ISI is a questionnaire widely used to assess nature, severity and impact of insomnia. It has 7 questions, which are summarized to a total score. The ISI will be completed electronically at Screening Visit, Baseline 1 and at Visit 1 (**AMS-ePRO®**).

9.1.14.3 Epworth Sleepiness Scale (ESS)

The ESS is a validated measure of the patient's general level of daytime sleepiness. The patient rates the chances to fall asleep in 8 different situations commonly encountered in daily life. The total ESS score is based on a scale of 0 to 24. The higher the score, the higher the patient's level of daytime sleepiness. The ESS will be completed electronically at Baseline 1 and at Visit 1 (**AMS-ePRO®**).

9.1.14.4 Würzburg Fatigue Inventory (WEIMuS)

The WEIMuS is a 17-item scale designed to assess fatigue as a symptom of a variety of different chronic conditions and disorders. The scale addresses fatigue's effects on daily functioning, querying its relationship to motivation, physical activity, work, family, and social life, and asking respondents to rate the ease with which they are fatigued and the degree to which the symptom poses a problem for them. The WEIMuS will be completed on paper at Baseline 1 and at Visit 1.

9.1.14.5 Short Form-36 Health Survey Version 2 (SF-36v2)

The SF-36v2 questionnaire (Short Form Health 36, version 2.0) questionnaire is a globally established, validated and frequently used questionnaire regarding the quality of life. It consists of 36 questions on general health. The SF-36v2 will be completed on paper at Baseline 1 and at Follow-up Visit.

9.1.14.6 Subclinical Stress Symptom Questionnaire-25 (SSQ-25)

The Subclinical Stress Symptom Questionnaire (SSQ-25) is a comprehensive, reliable, and valid instrument that allows a valid assessment and differentiation of subclinical stress symptoms. This questionnaire consists of 25 questions regarding symptoms following stressful events and will be completed on paper at Baseline 1 and at Follow-up Visit.

9.1.14.7 Primary Appraisal Secondary Appraisal (PASA)

Primary Appraisal Secondary Appraisal (PASA) assesses 4 anticipatory cognitive appraisal processes, threat, challenge, self-concept of own abilities and control expectancy. Each of these primary PASA scales comprises 4 items that are rated on a 6-point Likert scale ranging from strongly

disagree to strongly agree. The PASA will be completed electronically at Baseline 1 and at Visit 1 (**AMS-ePRO**[®]).

9.1.14.8 Perceived Stress Scale-10 (PSS-10)

The PSS (Cohen, Kamarck et al. 1983) is a widely used psychological instrument for measuring stress perception. It measures how unpredictable, uncontrollable, and overloaded individuals judge their lives within the last month. The English version of the PSS-10 comprises 10 items that are answered on a five-point rating scale ranging from 0 = 'never' to 4 = 'very often' and will be completed on paper at Baseline 1 and at Follow-up Visit. A German translation of the English PSS-10 version is used.

9.1.14.9 Beck's Depression Inventory-II (BDI-II)

The BDI-II is a 21-item, self-report rating inventory that measures characteristic attitudes and symptoms of depression. The BDI-II is a new revised edition of BDI and includes items intending to index symptoms of severe depression, which would require hospitalization. It will be completed on paper at Baseline 1 and at Visit 1.

9.1.14.10 Beck's Anxiety Inventory (BAI)

The BAI is a 21-item multiple-choice self-report inventory that measures the severity of anxiety in adults and adolescents. Because the items in the BAI describe the emotional, physiological, and cognitive symptoms of anxiety but not depression, it can discriminate anxiety from depression. The BAI will be completed on paper at Baseline 1 and at Follow-up Visit.

9.2 Safety Parameters

9.2.1 Adverse Events

Definition, collection and reporting of adverse events are described in section 10.

9.2.2 Vital Signs

Vital signs (heart rate, systolic/ diastolic blood pressure) will be collected at Screening Visit.

9.2.3 Physical Examination

At Screening Visit (Day -28 to -8) a physical examination will be performed. Physical status of cardiovascular, respiratory, musculoskeletal and gastrointestinal systems, head and eyes and other abnormalities, if applicable, will be recorded in the eCRF.

9.2.4 Safety Laboratory

Safety laboratory blood samples will be collected once at Screening Visit (and up to 2 working days later) using S-Monovette[®] Lithium-Heparin Gel (2.7 ml for CRP, liver enzymes and thyroid hormones), S-Monovette[®] GlucoEXACT (3.1 ml for blood glucose), S-Monovette[®] K3 EDTA (2.6 ml for complete blood count [CBC] with differential and Erythrocyte Sedimentation Rate [ESR]), totally 8.4 ml. Samples will be consecutively analyzed at the local routine laboratory of the investigational site, the Institut für Klinische Chemie und Laboratoriumsdiagnostik (IKCL), Jena University Hospital.

The following parameters will be analyzed:

- Complete Blood Count (CBC with differential)
- Thyroid hormones
- Blood glucose
- C-Reactive Protein (CRP)

- Erythrocyte Sedimentation Rate (ESR)
- Liver enzymes (ASAT, ALAT, gamma GT, alkaline phosphatase).

9.3 Appropriate ness of Measurements

All clinical procedures that will be used in this trial are standard and generally accepted.

10. Safety Reporting

10.1 Definitions

10.1.1 Adverse Event (AE)

According to ICH E2A an Adverse Event (AE) is defined as:

Any untoward medical occurrence in a patient or clinical investigation subject administered a pharmaceutical product and which does not necessarily have to have a causal relationship with this treatment.

An AE can therefore be any unfavorable and unintended sign (including an abnormal laboratory finding), symptom, or disease temporally associated with the use of an IMP, whether or not considered related to the IMP.

10.1.2 Treatment-Emergent Adverse Events (TEAE)

A treatment-emergent adverse event (TEAE) is defined as any event not present prior to the initiation of the treatment or any AE already present that worsens in either intensity or frequency following exposure to the treatment.

All AEs collected from visit Baseline 2 (Day -1 to 0) until 1 day (24 hours) following last IMP intake are considered as TEAEs in this clinical trial.

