At **Baseline 1** (Day -2 to Day -1) patients will have their first night at the trial site for PSG adaptation and screening for exclusion criterion 3. Patients complete their electronic sleep diary (adapted from DGSM, on **AMS-ePRO®**) to be kept until the End of Trial (Follow-up Visit/ Day 28+3) and questionnaires on sleep, mood, stress and quality of life. In the evening before the Baseline 1 night urine and breath alcohol tests will be conducted on drugs and alcohol, respectively. After awakening (Day -1) resting state stress parameters in saliva are to be collected (at 5 time points) and every 3 hours (at 4 time points). In the course of the morning, patients will perform neuropsychological tests from the TAP battery. An rsEEG and measurement of resting heart rate and HRV will be performed at approximately 15 minutes prior CPT. Around 12:00 at Day -1 a CPT will be conducted, before and afterwards blood samples will be collected. Patients will complete a subjective pain and stress rating during CPT test.

The following procedures will be performed:

- Urine collection for test on drugs in the evening at Day -2 (section 9.1.11)
- Breath alcohol test in the evening at Day -2 (section 9.1.11)
- Completion of the following questionnaires:
 - a) on paper: BAI, BDI-II, WEIMuS, PSQI, PSS-10, SF-36v2, SSQ-25
 - b) on **AMS-ePRO®**: ESS, ISI, PASA (section 9.1.14)
- PSG for screening of exclusion criterion 3 and for adaptation to the unfamiliar sleep lab environment in the night between Day -2 and Day -1 (section 9.1.1)
- Check exclusion criterion 3 at Day -1
- Collection of 0.5 to 1 ml saliva to measure cortisol, DHEA-S and alpha-amylase at awakening (0 minutes), and after 15 minutes, 30 minutes, 45 minutes, 60 minutes, 3 hours, 6 hours, 9 hours and 12 hours after awakening at Day -1 (section 9.1.2)
- Neuropsychological tests (TAP) at Day -1 (section 9.1.10)
- Resting state EEG, resting state HR and HRV to measure daytime performance at Day -1 (section 9.1.3)
- CPT around 12:00 including subjective pain rating and pain tolerance, heart rate and associated HRV measures, electrodermal activity, and EEG at Day -1 (section 9.1.7)
- Collection of approximately 12.5 ml blood for measuring cortisol, DHEA-S, adrenaline, noradrenaline, inflammation markers (IL-6 and TNF- α) prior to CPT, 20 minutes and 50 minutes after CPT at Day -1 (section 9.1.8)
- Adverse events at Day -2 (section 10)
- Changes in concomitant medication at Day -2

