- Complete sleep diary and stress assessment (in **AMS-ePRO®**).

At **Baseline 2** (Day -1 to Day 0) patients will stay at the site for a second night for PSG. After awakening (Day 0) resting state stress parameters in saliva are to be collected (at 5 time points). Patients will be randomly assigned to treatment group Neurexan® or Placebo with a 1:1 allocation and stratification by sex.

The following procedures will be performed:

- Urine collection for test on drugs in the evening at Day -1 (section 9.1.11)
- Breath alcohol test in the evening at Day -1 (section 9.1.11)
- Baseline 2 PSG night to measure primary, i.e., SE and secondary endpoints, i.e., SOL, WASO, TST, NWAK, and ARI during sleep in the night between Day -1 and Day 0 (section 9.1.1)
- Collection of 0.5 to 1 ml saliva to measure cortisol, DHEA-S and alpha-amylase at awakening (0 minutes), and at 15 minutes, 30 minutes, 45 minutes, 60 minutes after awakening at Day 0 (section 9.1.2)
- Adverse events at Day -1 and Day 0 (section 9.2.1)
- Changes in concomitant medication at Day -1 and Day 0
- Randomization to treatment group at Day 0 (section 11.2)
- Distribution of IMP and instruction regarding use of IMP at Day 0
- Starting IMP treatment after having performed all Baseline 2 assessments at midday Day 0 (section 7.1)
- Complete sleep diary and stress assessment (in **AMS**-ePRO®).

Patients will continue to take their trial treatment for 14 consecutive days (Day 0 - Day 13).

At **Visit 1** (Day 12 to Day 13; +2 days) patients return to the trial site for another PSG adaptation night. A urine and breath alcohol test will be conducted on drugs and alcohol, respectively. After awakening (Day 13) resting state stress parameters in saliva are to be collected (at 5 time points) and every 3-hours (at 4 time points). In the course of the morning, patients will perform neuropsychological tests from the TAP battery. An rsEEG and measurement of resting heart rate and HRV and EDA will be performed at approximately 15 minutes prior CPT. Around 12:00 at Day 13 a CPT will be performed, blood samples will be collected (before CPT and 20 minutes and 50 minutes after CPT) and patients will complete a subjective pain and stress rating. During CPT an EEG will be performed and heart rate and HRV will be measured. Additionally, patients will complete questionnaires on sleep, stress and quality of life on paper (BDI-II, WEIMuS) and on **AMS**-ePRO® (ESS, ISI, PASA).

The following procedures will be performed:

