11.3.2 Analysis Populations

Analyses will be based on the safety population, ITT population, and the Per-Protocol Population (PPP).

The screening population is defined as all patients who signed informed consent.

The safety population is defined as all patients who were randomized and received at least one dose of investigational medication. All safety analyses will be based on the treatment actually taken by the patient ('as treated').

The ITT population is defined as patients who were randomized and received at least one dose of investigational medication and had at least one post-dose assessment.

The Per-Protocol Population (PPP) is defined as all patients who received investigational treatment and fulfil the following criteria:

- The absence of any important major protocol deviations
- No technical difficulties during PSG
- Patients who were correctly stratified and received the correct treatment
- Sufficient treatment compliance of 80%-120%.

Treatment compliance will be defined via the amount of IMP that has been taken between first intake at Baseline 2/ second day and last intake at Visit 2/ first day in relation to the amount that should have been taken by a patient.

Protocol deviations will be collected during the entire trial and will be classified as minor or major at the BDRM. Protocol deviations that may affect the efficacy outcome of patients will be classified as major. The decision about major protocol deviations and assignments to populations will be taken in a blinded fashion and will be documented in the BDRM meeting minutes prior to unblinding of the trial.

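### Protocol section 10.1.2 counts adverse events from before the first dose as treatment-emergent, against its own definition

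*Protocol*

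**What the plan says.** Section 10.1.2 of the protocol gives two rules in succession.

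- **General definition.** A TEAE is "any event not present prior to the initiation of the treatment", or an existing event that gets worse once treatment has begun.
- **Rule for this trial.** "All AEs collected from visit Baseline 2 (Day -1 to 0) until 1 day (24 hours) following last IMP intake" are treated as TEAEs. This sentence has no condition on onset or on worsening.

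The timing of the first dose is stated elsewhere and is consistent. The Baseline 2 list in section 8.1 reads "Starting IMP treatment after having performed all Baseline 2 assessments at midday Day 0". The footnotes to the schedules in section 2.2 and Table 3 add that this follows randomization, and section 11.2 puts allocation after all baseline assessments. Section 11.3.2 defines compliance from "first intake at Baseline 2/ second day", which is also Day 0.

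On collection, the visit lists in section 8.1 name adverse events at Day -2 for Baseline 1, and at Day -1 and Day 0 for Baseline 2. Section 11.5 tabulates AEs and TEAEs as separate safety variables.

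**The concern.** The two rules disagree about any event that starts between the opening of Baseline 2 on Day -1 and midday on Day 0 and does not later worsen. Under the general definition it is not a TEAE; under the trial rule it is. Most of that interval also lies before randomization. A TEAE table is meant to isolate what happened on treatment, and events that precede the first tablet say nothing about the product.

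The trial rule also works by when an event is *collected*, not by when it began. The Baseline 1 schedule states: "Around 12:00 at Day -1 a CPT will be conducted". Sections 8.1 and 9.1.8 attach three blood draws to that test. By the visit lists, the first scheduled AE check after these pre-treatment procedures is at Baseline 2. A procedure-related event filed there becomes a TEAE; the same event filed under Baseline 1 does not.

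At stake is the accuracy of the descriptive safety summary. TEAE counts would be too high in both arms, and two programmers following different sentences of the same section would produce different tables.

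**Working it through.** The protocol gives no figure to reproduce. The check has two parts.

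**1. One event under both rules.** Take an event starting during the Baseline 2 polysomnography night and not worsening later.

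| Rule | Condition | Result |
|---|---|---|
| General definition, 10.1.2 | Absent before treatment, or worsens after exposure | Not a TEAE |
| Trial rule, 10.1.2 | Collected from Baseline 2 (Day -1 to 0) onward | TEAE |

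No other section settles which rule applies.

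**2. Pre-dose share of the window.**

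Inputs from the protocol:
- first intake at midday on Day 0 (section 8.1);
- last intake on the night of Day 13, before sleep (section 8.1);
- allowance of up to 2 further days (section 7.2);
- window end 24 h after last intake (section 10.1.2).

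Assumptions, because no clock times are given: last intake at 22:00; Baseline 2 opening at 18:00 on Day -1 (base case), 22:00 on Day -1 (latest) or 00:00 on Day -1 (earliest).

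Time from first intake to window end:
- 12:00 Day 0 to 22:00 Day 13 = 13 × 24 + 10 = 322 h;
- plus 24 h = 346 h;
- with the 2-day allowance, 346 + 48 = 394 h.

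Share = pre-dose hours / (pre-dose hours + hours from first intake).

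| Baseline 2 opens | Pre-dose hours | No allowance | With 2 extra days |
|---|---|---|---|
| 22:00 Day -1 | 14 | 14/360 = 3.9% | 14/408 = 3.4% |
| 18:00 Day -1 | 18 | 18/364 = 4.9% | 18/412 = 4.4% |
| 00:00 Day -1 | 36 | 36/382 = 9.4% | 36/430 = 8.4% |

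Moving the last intake to 21:00 or 01:00 changes these by less than 0.1 percentage point.

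**Counts of procedures.** The window contains three polysomnography nights (Baseline 2, Visit 1, Visit 2), and the first is pre-dose. If Day -1 procedure events are recorded at Baseline 2, the window takes in the consequences of 2 Cold Pressor Tests and 6 associated blood draws, against 1 and 3 after first intake.

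**Residual after the fix.** Section 10.4 lists start dates for AEs, not times. If Day 0 events of unknown time stay in, at most 12 pre-dose hours remain: 12/358 = 3.4%, or 12/406 = 3.0% with the allowance.

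**The case against.** The best counter-argument is that this is a drafting slip with little consequence. The bracketed days repeat the schedule's label for Baseline 2, which is also the visit of first intake. Safety is descriptive, all events are listed, start dates are recorded, and the extra events fall before dosing in both arms. Section 11.3 allows the SAP to modify protocol plans. This limits the consequence but does not reconcile the two sentences: the bracket expressly includes the day before dosing.

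The Cold Pressor Test argument is conditional. AE recording runs continuously from consent (sections 8.1 and 10.3), patients also report events in the daily diary (section 9.1.9), and procedure relatedness is captured separately (section 10.4.2). An event from the Day -1 test may therefore be recorded before Baseline 2, and would in any case carry a procedure flag. That stands. It also means that classification would depend on when an event was written down, and the procedure flag does not remove it from the TEAE count.

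The hour shares are not shares of events, and the 9.4% case has weak support: the Baseline 2 procedures with a stated time on Day -1 are in the evening, and the daytime work belongs to Baseline 1. Both points are fair. The percentages describe the window only.

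**Conclusion.** The concern holds. Section 10.1.2 contradicts itself, and the trial-specific rule is wrong as written because it labels pre-dose events treatment-emergent. About 5% of the window is pre-dose if Baseline 2 opens in the early evening of Day -1, with a range of 3.4% to 9.4% over the assumed clock times. The protocol gives no AE rate, so no number of misclassified events can be stated. The consequence is confined to over-counting in a descriptive table in both arms, with no expected bias toward either and no effect on the primary analysis. It should be corrected before database lock.

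**What to change.** Replace the second sentence of section 10.1.2 with a rule based on onset: a TEAE is an AE with onset, or a pre-existing AE that worsens, at or after first IMP intake on Day 0 and up to 24 hours after the last intake. Report AEs with earlier onset separately as pre-treatment events. Keep Day 0 events of unknown onset time as TEAEs, as the conservative choice, and carry the same wording into the SAP.

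The cost is one sentence. No new assessment is needed, since section 10.4 already records AE start dates and the start of medication. The remaining weakness is the Day 0 residual of at most 12 hours, about 3% of the window, so in the base case the pre-dose time falls from 18 to 12 hours and not to zero. All events with onset on Day -1, including those from the Cold Pressor Test, leave the TEAE count unless they later worsen on treatment.
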